## **Safety Reporting**

The study drug, benralizumab, is an off-label indication for subjects recruited for this study. The Principal Investigator will therefore submit expedited reports, as indicated/necessary for reporting of serious adverse drug reactions, by fax, directly to Health Canada Biologics and Genetic Therapies Directorate.

Adverse drug reactions that are *both serious and unexpected* are subject to expedited reporting to Health Canada. Expedited reporting of reactions which are serious but expected is not required. Expedited reporting is not required for serious events from clinical investigations that are considered unrelated to the study product, whether or not the event is expected.

In accordance with Health Canada requirements, an Adverse Drug Reaction Report will be filed in the cases

- where the adverse drug reaction is neither fatal nor life-threatening, within 15 days after becoming aware of the information;
- where adverse drug reactions is fatal or life-threatening, immediately where possible and, in any event, within 7 days after becoming aware of the information;
- within 8 days after having informed Health Canada of the adverse drug reactions, submit as complete as possible, a report which includes an assessment of the importance and implication of any findings

All safety reports submitted to Health Canada will also be submitted to AstraZeneca at the following address: [[contact]](mailto:[contact]).

## **Procedures**

### *Skin Prick Test*

A skin prick test will be used to determine the allergen(s) to which each subject is sensitized.

Standard allergen extracts will include ragweed, trees, grass, dog, cat, horse, dust mites (*Dermatophagoides farinae* and *D. pteronyssinus*), *Alternaria*, and *Aspergillus*. Extracts will be applied to the back then pricking the skin to allow exposure, and then evaluating the local reaction in the skin. A positive control (1 mg/mL histamine) and a negative control (diluent) are applied to the skin. If an allergen provokes an allergic reaction, a raised itchy bump (wheal)

develops. The size of the wheal (the raised area, not the redness) will be measured and recorded with a ruler in millimeters in the horizontal and vertical directions, perpendicular to each other after approximately 15 minutes. The size of the wheal for each antigen will be recorded on the Skin Test Form, along with any observed adverse reaction or event and any actions taken.

A reaction greater than  $2 \times 2$  mm will be regarded as positive, provided that the positive and negative controls are appropriately positive (histamine) and negative (diluent), respectively. The investigator is to choose an allergen for injection on the basis of the skin response. The investigator may choose to perform a RAST test to assist with selection of an appropriate allergen. This procedure will be completed in accordance with the allergen skin testing using the epicutaneous method SOP at McMaster University (Hamilton, Ontario, Canada).

Allergen extracts manufactured following GMP guidelines, will be selected, prepared by staff and administered to the subjects by injection in accordance with procedures approved by Health Canada.

#### *Intradermal Allergen Challenge*

[figure not shown]
The allergen extract selected for intradermal testing will be determined by the results of the skin prick test, being the allergen that gives the largest skin wheal. The selected allergen will be injected in a volume of 100  $\mu$ L intradermally in two adjacent and standardized locations on the subject's back. A saline control will also be injected in a volume of 100  $\mu$ L intradermally in one location of the subject's back. At 24 hours after challenge, the size of the wheal and flare will be measured, and a punch biopsy will be taken from the centre of the sites (2 allergen, 1 diluent) plus an adjacent unchallenged/unaffected site.

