#### *Follow-up*

Patients will return for a safety follow-up visit on study Day 140 (week 20), which is 12 weeks after the last dose/11 weeks after the last study procedure.

*Figure 1 - Study flow chart.*

Randomized double-blind, placebo-controlled, parallel-group prospective study. Patients with a history of atopic dermatitis will enter a screening period to assess responses to intradermal allergen challenge. Those developing a late cutaneous response 24 hours later will have the size of the wheal/flare measured and a punch biopsy obtained from the challenge site for measurement of eosinophils and basophils. Patients will then be randomized 1:1 to benralizumab (30 mg SC monthly) or placebo, with dosing at days 0, 28 and 56. Blood and a sample of a skin lesion will be collected on Day 0 before dosing. A skin lesion will be collected at Day 28 and blood will be collected again 65 days after the first dose, for assessments of eosinophils, basophils and other cells including eosinophil progenitors, ILC2s, hemopoietic progenitor cells and CD4+ T cells. On Day 64 an intradermal allergen challenge will be conducted and on Day 65 the size of the wheal/flare will be measured and a punch biopsy will be obtained from the challenge site for a measurement of eosinophils and basophils. Skin lesions will be assessed clinically before dosing and throughout the study using the EASI score. A safety follow up visit will take place at week 20, which is 140 days after the first dose (12 weeks after the last dose). Each visit has a +/- 3 day window with the exception of Day 0 and Day 65 which must take place exactly 1 day after Day -1 and Day 64, respectively.

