### **Inclusion Criteria**

The following inclusion criteria must be met for to enter the screening phase of the study:

1. Male and female patients 18 through 65 years of age.
2. Women of childbearing potential (WOCBP) must not be actively seeking pregnancy, and must use an effective form of birth control (confirmed by the Investigator). Effective forms of birth control include: true sexual abstinence, a vasectomized sexual partner, Implanon, female sterilization by tubal occlusion, any effective IUD intrauterine device/IUS levonorgestrel Intrauterine system, Depo-Provera™ injections, oral contraceptive, and Evra Patch™ or Nuvaring™. WOCBP must agree to use effective method of birth control, as defined above, from enrolment, throughout the study duration and within 16 weeks after last dose of IP. They must demonstrate a negative serum pregnancy test at screening and demonstrate a negative urine pregnancy test immediately before each dose of study drug or placebo. Women not of childbearing potential are defined as women who are either permanently sterilized (hysterectomy, bilateral oophorectomy, or bilateral salpingectomy), or who are postmenopausal. Women will be considered postmenopausal if they have been amenorrheic for 12 months prior to the planned date of randomization without an alternative medical cause. The following age-specific requirements apply:

- Women <50 years old would be considered postmenopausal if they have been amenorrheic for 12 months or more following cessation of exogenous hormonal treatment and follicle stimulating hormone (FSH) levels in the postmenopausal range.
- Women ≥50 years old would be considered postmenopausal if they have been amenorrheic for 12 months or more following cessation of all exogenous hormonal treatment.

3. All male patients who are sexually active must agree to use an acceptable method of contraception (condom with or without spermicide, vasectomy) from the first dose of IP until 16 weeks after their last dose.
4. General good health
5. Moderate to severe atopic dermatitis
6. Able to understand and give written informed consent and has signed a written informed consent form approved by the investigator's REB

The following inclusion criteria must be met for entry into the dosing phase of the study:

1. Positive skin-prick test to common aeroallergens (including cat, dust mite, grass, pollen)
2. Positive late cutaneous response to intradermal allergen challenge

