### *Secondary endpoints*

1. The number of basophils per millimetre squared of skin, measured 24 hours post intradermal allergen challenge, after 65 days of dosing. The number of basophils in the skin will be assessed by immunohistochemistry of a punch skin biopsy obtained from the site of the intradermal allergen challenge, using a commercial antibody specific for basophils.
2. The size of the late cutaneous response, measured 24 hours post intradermal allergen challenge, 65 days after the first dose. The late cutaneous response will be calculated using the length and width of the wheal and flare response to a standardized amount of allergen extract.
3. Eczema Area and Severity Index (EASI) score.

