#### **Statistical methods**

Using data from a study with the same model (intradermal allergen challenge) in the same patient population (moderate-to-severe atopic dermatitis), the sample size requirement was determined using data collected from 7 subjects undergoing identical challenge protocols in our laboratory in an ongoing study of the protective effects of prednisone treatment. In the 4 prednisone-treated subjects the mean increase in skin eosinophils during the screening portion of the study was 59.8 (42.9) [cells/mm^2;M(SD)]. This was reduced to 16.25 (20.6) during the prednisone treatment period. The mean % reduction in the delta between the screening and prednisone challenges was 80.4 (41.5). To calculate the sample size for the current study, we have assumed that treatment with benralizumab will yield a similar protective effect as prednisone, and that there will be a similar between subject variability in this protective effect. We also assumed that there will be no protective effect in the placebo arm, but that the variability in that arm will be similar to that seen in the treatment arm. Thus, using projected mean % reduction in the delta eosinophils of 80 in the prednisone arm, 0 in the placebo arm with a SD of 40 in both of those arms, a sample size of 6 would be needed to demonstrate statistical difference

using an independent Student t-test. We have chosen to put 10 subjects into each arm to allow for subject drop out and also to give increased power for secondary mechanism based investigations.

The primary analysis will be on the % reduction of the allergen induced increase in tissue eosinophils. The allergen induced increase in tissue eosinophils will be calculated by subtracting the cell count made with saline from the count made with allergen 24h post challenge. This will be performed during the screening phase (Day 0) and the treatment phase (Day 65) of the study. The percent reduction will be calculated by expressing this increase in the treatment phase as a percentage of that in the screening phase. The percent increases during the placebo and active treatment arms of the study will be compared using an independent Student t-test.

Statistical significance will be set at  $p < 0.05$ .

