**Study Schematic**

Study Procedures	Visit 1 Day -1	Visit 2 Day 0	Visit 2b Day 14	Visit 3 Day 28	Visit 4 Day 56	Visit 5 Day 64	Visit 6 Day 65	Visit 7 Day 140
Physical Exam/Medical History	x							
Vital Signs	x	x		x	x	x	x	x
Examination of Skin	x							
Examination of contralateral lesion		x	x	x	x		x	
Skin Prick Test	x					x		
Patient Questionnaires: EASI, IGA, SCORAD, DLQI, POEM, PGAD			x	x	x	x		
Blood Sample Safety Efficacy		x	x				x	x
Urine Sample Safety Pregnancy	x		x*		x*	x*		x
Intradermal challenges	x					x		
Skin biopsies From intradermal challenges From lesion		x	x	x			x	
Drug administration		x		x	x			

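### Could the Day 64 challenge use a different allergen from the one given at screening, and so spoil the primary ratio?

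*Combined protocol and SAP*

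**What the plan says.** Three places bear on how the allergen is chosen.

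- **Intradermal Allergen Challenge:** the extract is "determined by the results of the skin prick test, being the allergen that gives the largest skin wheal". The visit of the governing test is not named.
- **Skin Prick Test (Procedures):** "The investigator is to choose an allergen for injection on the basis of the skin response", with an optional RAST test to help.
- **Study Schematic:** the row "Skin Prick Test" is marked at Visit 1 (Day -1) and Visit 5 (Day 64), the same two visits as the intradermal challenges.

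The later challenge appears in the Figure 1 text only as "On Day 64 an intradermal allergen challenge will be conducted". The secondary endpoint for the late response refers to "the length and width of the wheal and flare response to a standardized amount of allergen extract", which fixes the amount but not the identity of the extract. One of the two criteria for entering the dosing phase is "Positive late cutaneous response to intradermal allergen challenge".

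Statistical methods defines the primary variable from the allergen-minus-saline eosinophil count at each of the two challenges: "The percent reduction will be calculated by expressing this increase in the treatment phase as a percentage of that in the screening phase".

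**The concern.** The ratio isolates treatment only if the stimulus is the same on both occasions. The prick test has one stated use, to find the patient's sensitizations so that a challenge allergen can be chosen, and the schematic repeats it on the day of the second challenge. Someone applying the largest-wheal rule literally on Day 64 could choose a different extract. That extract would not have been shown to produce a late response in that patient, because the entry criterion was met with the screening allergen. A low Day 65 count might then reflect a weaker stimulus rather than the drug.

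If switching were equally common in both arms, the cost would be extra noise and lost power. Bias between arms would require treatment to change which allergen gives the largest wheal. Nothing in the documents shows that.

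**Working it through.** **1. The plan's own sample size.** Inputs from Statistical methods: reduction 80 versus 0, SD 40 in each arm, Student t-test, 0.05 (taken as two-sided). Power is the probability that a noncentral t variable with 2n - 2 degrees of freedom and noncentrality 80 / (40 × √(2/n)) falls outside the critical values.

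| n per arm | Noncentrality | Critical t | Power |
|---|---|---|---|
| 5 | 3.162 | 2.306 | 79% |
| 6 | 3.464 | 2.228 | 87.6% |
| 10 (planned) | 4.472 | 2.101 | 98.8% |

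Six per arm is the smallest size with at least 80% power, so the stated 6 reproduces.

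**2. What the text implies.** The prick test and the late response to the intradermal challenge are both conditions for entering dosing, so the allergen must be chosen before treatment starts. The Intradermal Allergen Challenge section speaks in the singular of one prick test and one chosen allergen. Statistical methods then defines one quantity, obtains it twice in the same patient and takes a ratio, which makes sense only with the same stimulus. The Day 64 prick test appears in the schematic alone. Some multi-line rows of that table are misaligned in the copy reviewed, but this row is a single line and matches the intradermal row, so the mark is probably correct. It still does not say that the second test re-selects.

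**3. How often a switch could occur.** With one selection at screening, or with only one positive allergen, the answer is none. Under strict re-selection a model is needed, and every input is assumed: true wheals with mean 6 mm and SD 2 mm, reading SD 0.75 to 1.5 mm. The largest wheal then changes in 16% to 28% of patients with two positive allergens and 28% to 46% of those with four. The top of that range is about 9 of 20.

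**4. What switching would cost.** Let the Day 65 increase as a percentage of screening be normal with SD 40, mean 100 on placebo and 20 on active. A reduction is 100 minus this figure, so the t-test is unchanged. In a switched patient, multiply by a lognormal factor with mean 1.0 or 0.5 and CV 0.36 or 0.72. The 0.72 is 42.9/59.8, the between-patient CV of the screening increase in four subjects; 0.36 is half of it. Power by simulation (40,000 trials per cell):

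| Switched, both arms | 10 per arm, planned effect | 6 per arm, planned effect | 10 per arm, effect of 50 points |
|---|---|---|---|
| 0% | 99% | 88% | 75% |
| 16% | 96-98% | 79-86% | 64-72% |
| 28% | 94-98% | 72-84% | 56-69% |
| 47% | 89-97% | 64-82% | 46-66% |

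Type I error with 10 per arm is 4.3% to 5.1% throughout.

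**5. Hand check of one cell.** With factor mean 1, CV c and switched share q, the variance in an arm with mean m is 40² + q × c² × (m² + 40²). For q = 0.47 and c = 0.36:

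- placebo: 1600 + 0.47 × 0.1296 × 11,600 = 2307
- active: 1600 + 0.47 × 0.1296 × 2000 = 1722

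The pooled SD is √((2307 + 1722)/2) = 44.9, which gives noncentrality 80 / (44.9 × √0.2) = 3.98 and power of about 96%. The simulation gives 97%.

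**6. A harsher assumption.** With a lognormal factor of median 1 and log-SD 1.0, the CV is √(e - 1) = 1.31, about 1.8 times the between-patient CV. Power at 10 per arm is then 91.8% with 10% switched and 66.7% with 50% switched. With log-SD 0.5 the same range of switching gives 97.9% to 93.3%.

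**The case for a change.** The best case for a change is that the silence is real, touches the stimulus behind the primary variable in a 20-patient trial, and cannot be repaired after Day 64. The Day 64 prick test has no stated purpose, so staff following the text literally might re-select. The planned effect comes from four prednisone-treated subjects and is only assumed to carry over to benralizumab. With a weaker effect or fewer evaluable patients there is less power to spare, as the last two columns of the table show. A clarifying sentence would cost almost nothing.

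What stands is the silence itself: no available section states that the extract is carried forward. The institutional skin-testing procedure cited under Skin Prick Test, which might settle it, is not among the documents.

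The rest is weaker. The two readings are not equally natural, for the reasons in step 2. Six per arm is not the planned analysis size: the plan calls for 20 evaluable subjects and replaces those who drop out before the primary assessment. The 50-point effect appears nowhere in the documents, and it alone takes power from 99% to 75% before any switching. The low ends of the ranges also pair poorly with the switch model. Patients switch mainly when two wheals are nearly equal, which gives little reason to expect the replacement to halve the response. A between-patient CV also includes differences in patient responsiveness that a within-patient switch would not add. Wheal size is not eosinophil count, so this does not exclude a larger effect, but nothing in the documents supports one.

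**Conclusion.** The concern does not call for a change. The plan states no wrong rule. It leaves unsaid something that its entry criteria and its within-patient ratio already imply, and that an allergen-challenge laboratory would be expected to do: reuse the screening allergen. On that reading no patient switches and nothing is lost.

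If allergens were re-selected equally in both arms, the test would remain valid. Power at the planned effect and 10 per arm would stay at about 89% to 98% for 16% to 47% switched, with a factor CV of up to 0.72. It would fall to about 67% only if half the patients switched and the spread between allergens within a patient were much wider than the spread between patients in the pilot data. The switch rates and the spread are assumptions, since the documents give neither. No bias between arms is shown, and the primary endpoint as worded under Efficacy Endpoints, the Day 65 count, has no screening denominator.

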#### *Skin Sampling*

Punch biopsies will be obtained from the site of the intradermal allergen (A) and saline (S) challenges and an unaffected site (U) adjacent to intradermal challenges using a sterile 4 mm skin punch by applying and twisting until the blade of the skin punch has pierced the skin. The biopsy will be removed using sterile forceps and a scalpel. These samples will be processed for histologic examination of inflammatory cells, including eosinophils, mast cells and basophils.

A skin lesion (L) will be sampled by excising not more than 1 cm x 3 cm using a sterile scalpel. These skin biopsies will be analyzed for inflammatory cells including eosinophils, eosinophil progenitors, basophils and mast cells. If the lesion is too small to obtain sufficient cell numbers

for flow cytometry, only a punch biopsy will be obtained for microscopy. A second skin lesion on the contralateral side will be identified for observation throughout the study (measure size, photograph, conduct EASI assessment at each visit).

*Figure 2 – Site of skin biopsies*

Before a biopsy is taken, the skin is thoroughly cleaned and local anesthetic (2% lidocaine) is injected to numb the skin. The site of skin biopsies and excision will be sutured and covered with a sterile bandage. Subjects will be instructed how to keep the site clean, and sutures will be removed at the next study visit.

#### *Blood Sampling*

At visit 1 (D-1, screening) and visit 7 (D140) blood will be collected for safety labs including complete blood count, coagulation, and chemistry including alanine aminotransferase and aspartate aminotransferase. At visit 1 blood will also be collected for virology (hepatitis B and C, and HIV). Incidental findings would be given the appropriate medical follow up. Women will have blood drawn for pregnancy testing or FSH to confirm a woman is post-menopausal. At visits 2 (D0) and 6 (D65), 30 mL of blood will be drawn from a vein in the arm using aseptic techniques. The blood will be used to measure circulating levels of inflammatory cells, including eosinophils, basophils and eosinophil/basophil progenitors. Those performing patient and laboratory assessments will remain blinded to the results of the blood cell counts.

#### *Urine Sampling*

At visit 1 (screening) and visit 8 (follow up) urine will be collected for safety urinalysis. After enrolment, urine will be collected from women at visits 2, 3 and 4 before dosing for urine pregnancy testing.

#### *Eczema Area and Severity Index*

The EASI is a validated measure used in clinical practice and clinical trials to assess the severity and extent of atopic dermatitis. It is a composite index with scores ranging from 0 to 72. Four atopic dermatitis disease characteristics (erythema, thickness [induration, papulation, edema], scratching [excoriation], and lichenification) will each be assessed for severity by the investigator or designee on a scale of “0” (absent) through “3” (severe). In addition, the area of AD involvement will be assessed as a percentage by body area of head, trunk, upper limbs, and lower limbs, and converted to a score of 0 to 6. In each body region, the area is expressed as 0, 1 (1% to 9%), 2 (10% to 29%), 3 (30% to 49%), 4 (50% to 69%), 5 (70% to 89%), or 6 (90% to 100%).

#### **Statistical methods**

Using data from a study with the same model (intradermal allergen challenge) in the same patient population (moderate-to-severe atopic dermatitis), the sample size requirement was determined using data collected from 7 subjects undergoing identical challenge protocols in our laboratory in an ongoing study of the protective effects of prednisone treatment. In the 4 prednisone-treated subjects the mean increase in skin eosinophils during the screening portion of the study was 59.8 (42.9) [cells/mm^2;M(SD)]. This was reduced to 16.25 (20.6) during the prednisone treatment period. The mean % reduction in the delta between the screening and prednisone challenges was 80.4 (41.5). To calculate the sample size for the current study, we have assumed that treatment with benralizumab will yield a similar protective effect as prednisone, and that there will be a similar between subject variability in this protective effect. We also assumed that there will be no protective effect in the placebo arm, but that the variability in that arm will be similar to that seen in the treatment arm. Thus, using projected mean % reduction in the delta eosinophils of 80 in the prednisone arm, 0 in the placebo arm with a SD of 40 in both of those arms, a sample size of 6 would be needed to demonstrate statistical difference

using an independent Student t-test. We have chosen to put 10 subjects into each arm to allow for subject drop out and also to give increased power for secondary mechanism based investigations.

The primary analysis will be on the % reduction of the allergen induced increase in tissue eosinophils. The allergen induced increase in tissue eosinophils will be calculated by subtracting the cell count made with saline from the count made with allergen 24h post challenge. This will be performed during the screening phase (Day 0) and the treatment phase (Day 65) of the study. The percent reduction will be calculated by expressing this increase in the treatment phase as a percentage of that in the screening phase. The percent increases during the placebo and active treatment arms of the study will be compared using an independent Student t-test.

Statistical significance will be set at  $p < 0.05$ .

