## **Efficacy Endpoints**

### *Primary endpoint*

1. The number of eosinophils per millimetre squared of skin, measured 24 hours post intradermal allergen challenge, 65 days after the first dose. The number of eosinophils in the skin will be assessed by histological examination of a punch skin biopsy obtained from the site of the intradermal allergen challenge.

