### *Patient recruitment*

The atopic dermatitis patient population is in need of an effective therapeutic for management of their disease, and these patients are readily accessible from [name] outpatient dermatology clinic. [name] manages over 100 patients with atopic dermatitis who are eager to test a new medication for control of their disease. Based on routine clinical patch testing, we anticipate the majority of patients with moderate to severe atopic dermatitis will develop late cutaneous responses to intradermal allergen challenge, and will develop elevated levels of eosinophils and basophils following intradermal allergen challenge (Macfarlane 1999). We do not anticipate any issues with recruitment or eligibility.

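### The primary t-test divides by a screening eosinophil increase that nothing in the plan keeps positive or away from zero, so one patient with a low value can decide the result

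*Combined protocol and SAP*

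**What the plan says.** The Statistical methods section defines the allergen-induced increase at each phase by "subtracting the cell count made with saline from the count made with allergen 24h post challenge". The primary variable is then a ratio of two such increases: "The percent reduction will be calculated by expressing this increase in the treatment phase as a percentage of that in the screening phase". The arms, 10 patients each, are compared by an independent Student t-test at the 5% level. As worded, the sentence gives the percentage remaining rather than the percentage reduction. The t-test p-value is the same for either, so this does not matter here.

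The only entry criterion tied to the challenge result is "Positive late cutaneous response to intradermal allergen challenge" (Inclusion Criteria), which the study flow chart describes by wheal and flare, not by cell count. The Patient recruitment section anticipates that most of the clinic's patients with moderate-to-severe disease "will develop elevated levels of eosinophils and basophils following intradermal allergen challenge", but this is an expectation and not a criterion. The screening biopsy is taken on Day 0, the day of the first dose, and no step makes dosing depend on its count. The Intradermal Allergen Challenge section provides two allergen sites but only one saline site.

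The Primary endpoint section names a different variable with no denominator: "The number of eosinophils per millimetre squared of skin, measured 24 hours post intradermal allergen challenge, 65 days after the first dose".

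**The concern.** The denominator is a difference between biopsy counts, and its saline term rests on a single site. If it is zero, the patient's outcome is undefined. If it is negative, the sign reverses. If it is small, the ratio becomes very large. The plan has no minimum, no handling rule, no transformation, no rank test and no sensitivity analysis.

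With 10 patients per arm, one extreme ratio shifts the arm mean and inflates the pooled SD, so a clear effect can become non-significant. Without a rule, the handling of that patient would be decided after the data are seen.

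**Working it through.** **Inputs.** All are from Statistical methods: reductions of 80 and 0, SD 40, 10 per arm; pilot screening increase 59.8 (SD 42.9) cells/mm², on-treatment increase 16.25 (SD 20.6), percent reduction 80.4 (SD 41.5), n = 4. Assumptions: a two-sided test (the plan does not say), the shape of the distributions, and the correlation between screening and Day 65.

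**1. The plan's sample size reproduces.** The normal formula n = 2(1.96 + 1.28)² × (40/80)² = 5.25 gives 6 per arm at 90% power. The exact t calculation gives power 0.790 at 5 per arm, 0.876 at 6 and 0.988 at 10. So 98.8% is what 10 per arm would deliver if the ratio really had SD 40.

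**2. One patient.**
- Base case: t = 80 / (40 × √(2/10)) = 4.47, p = 0.0003.
- Replace one mid-rank benralizumab patient by one with screening 5 and Day 65 16.25: score 100 × (1 − 16.25/5) = −225%. The arm mean falls by about (80 + 225)/10 = 30.5, the difference becomes 49 to 50, and p = 0.17 to 0.18.
- With screening −5 the same patient scores 100 × (1 + 16.25/5) = +425%, which would read as a very large benefit.
- Replace one placebo patient by one with screening −5 and Day 65 60: the ratio is −1200%, the arm difference becomes −49.5 (reversed) and p = 0.71.
- Significance is lost when a single screening increase falls to about 7 to 8 cells/mm² (Day 65 increase 16.25 on benralizumab or 60 on placebo).

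**3. What the pilot shows.** If none of four reductions exceeds 100% and their mean is 80.4, the SD is largest for {100, 100, 100, 21.6}: √[(3 × 19.6² + 58.8²)/3] = 39.2 (at most 39.3 allowing for rounding). The plan reports 41.5. At least one pilot reduction therefore exceeded 100%, so one subject had increases of opposite sign at the two phases. A negative difference did occur among four subjects. It need not have been at screening: screening 123.2, 28.4, 43.0, 44.5 with treatment 37.6, −11.9, 18.8, 20.4 reproduces the pilot summaries to rounding.

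**4. How often the denominator is low.** From 59.8 (42.9):
- Normal: P(≤ 0) = Φ(−59.8/42.9) = 8.2% per patient, and 1 − 0.918²⁰ = 82% for at least one of 20.
- Gamma: P(< 6) = 1.9% per patient, 32% for at least one of 20.
- Lognormal: P(< 6) = 0.06% per patient, 1.2% for at least one of 20.

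**5. Power at 10 per arm.** Simulated with screening and placebo Day 65 at 59.8 (42.9) and benralizumab Day 65 at 16.25 (20.6), 10,000 trials per cell. Paired figures are for correlations 0.5/0.7. HC3 is a small-sample robust standard error.

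| Increases | Ratio t-test | ANCOVA, HC3 |
|---|---|---|
| Normal | 25%/35% | 80%/90% |
| Normal, screening > 0 | 46%/60% | 83%/93% |
| Normal, screening > 10 | 70%/84% | 85%/94% |
| Normal, screening > 20 | 80%/92% | 86%/96% |
| Lognormal plus noise of 10 cells/mm² | 65%/74% | 84%/90% |
| Same, screening > 10 | 83%/94% | 83%/91% |
| Strictly positive lognormal | 94%/99% | 88%/94% |

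Over correlations 0 to 0.9, dropping the patient with the smallest absolute screening increase changed significance in 17–27% of trials (normal), 0–18% (gamma) and 0–14% (lognormal).

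**6. False positives.** With equal arms the ratio t-test rejects in 2.2–4.7% of null trials, ordinary ANCOVA in 4.4–5.5% and HC3 in 2.7–4.2%. With Day 65 SDs of 42.9 and 20.6 under the null, ordinary ANCOVA reaches 5.5–8.4% and HC3 3.9–6.5%, which is the reason for HC3.

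**The case against.** The p = 0.18 example is a chosen case. It pairs a screening increase of 5 with the average on-treatment value, whereas the power runs assume correlations of 0.5 and 0.7. At those values the expected on-treatment increase is 16.25 − 0.5 × (20.6/42.9) × 54.8 = 3.1, or −2.2 at 0.7. The scores would be 38% and 143%, with p = 0.0006 and 0.0002. This is right about the expectation. A value of 16.25 is still only about 0.7 residual SD above it at correlation 0.5, so the event can happen.

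The recruitment statement about most patients describes the clinic before selection, and the late-response criterion probably removes some low responders. That stands, but a skin response is not an eosinophil threshold.

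The pilot's negative difference may have been on treatment, where it does little harm. That also stands: the pilot shows that negative differences occur, not that a denominator was negative.

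The worst power figures come from unbounded normal distributions fitted to four subjects, and with strictly positive lognormal increases the planned test is better. ANCOVA is not uniformly strong either: in the normal scenario at zero correlation, HC3 power is about 70%, below an unadjusted t-test on the Day 65 increase (78%). The ratio test has about 14–15% there.

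Finally, ANCOVA changes the quantity estimated from a mean percentage to an absolute difference. That is a real change, although it moves closer to the stated primary endpoint.

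**Conclusion.** The concern holds and should be fixed. The missing rule and the unprotected denominator are facts of the plan. That one patient can overturn the result at 10 per arm is arithmetic. How likely this is cannot be settled from the documents, because they give neither the distribution nor the correlation: the power lost by the planned test runs from more than 50 points to none, and in the most favourable case the planned test is ahead by 5 to 6 points. The choice is lopsided in favour of not dividing. The consequence is lost power and a distorted or sign-reversed estimate; false positives are not inflated.

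**What to change.** In Statistical methods, make the primary analysis an ANCOVA:
- Response: Day 65 allergen-minus-saline eosinophils/mm². Factor: treatment. Covariate: the screening allergen-minus-saline value. Include all patients whatever the sign of the screening value.
- Use HC3 standard errors, because SDs and slopes may differ by arm. Report the adjusted difference with a 95% CI, and derive any percentage from the adjusted arm means (1 − benralizumab/placebo).
- Pre-specify a rank ANCOVA (Quade) as a sensitivity analysis and keep the per-patient percentage as supportive.
- Align the Primary endpoint wording, and restate the sample-size paragraph on this scale with the assumed correlation and a range around it.

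The cost is wording in two sections; no extra patients or samples are needed. If screening increases are all clearly positive and lognormal, ANCOVA gives up about 3 points of power with ordinary and 5 to 6 with HC3 standard errors. The rank ANCOVA gives up none there (98%/99.6%).

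If the percentage stays primary, state before unblinding how zero, negative and very small screening increases are handled, and replace the t-test with a rank test. This recovers only part of the loss: 55%/69% in the normal scenario.
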